6.3 PRIMARY ENDPOINTS

1. Population PK analysis of maltol and maltol glucuronide in plasma from PK samples collected on Day 1 (after first morning dose) and Day 10 (after last morning dose). Parameters to be derived and reported for each Ferric Maltol dose will be:

C_{max} , $C_{ave(0-6h)}$, $AUC_{(0-6h)}$, $AUC_{(0-inf)}$ on Day 1 and Day 10, and ratios of Day 10/Day 1 for these parameters.

T_{max} , half-life ($t_{1/2}$).

Apparent systemic clearance (CL/F), apparent volume of distribution (V/F).

Descriptive statistics for plasma concentrations of maltol and maltol glucuronide by time of collection on Day 1 and Day 10 will also be presented, including C_{trough} .

2. Descriptive and population PK analysis of serum iron and TSAT from PK samples collected on Day 1 and Day 10. Parameters to be derived and reported for each Ferric Maltol dose will be:

Change from pre-dose (C_{trough}) to maximum post-dose (C_{max}) value for serum iron and TSAT; $C_{ave(0-6h)}$.

Pre-dose adjusted Incremental $AUC_{(0-6h)}$ on Day 1 and Day 10 from a population PK analysis approach, and percentage change from Day 1 to Day 10.

Apparent systemic clearance (CL/F), apparent volume of distribution (V/F).

Descriptive statistics for serum iron and TSAT by time of collection on Day 1 and Day 10 will also be presented.

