8.1 INVESTIGATIONAL MEDICINAL PRODUCT (IMP) PRESENTATION

Ferric Maltol is presented as a hard, gelatine, red capsule. For the purposes of this study capsules containing three different doses of iron and associated excipients will be provided:

- 30 mg capsule: Each capsule contains 30 mg iron and the following excipient(s) with known effect: lactose, Allura Red AC (E129) and Sunset Yellow FCF (E110).
- 16.6 mg capsule: Each capsule contains 16.6 mg iron and the following excipient(s) with known effect: lactose, Allura Red AC (E129) and Sunset Yellow FCF (E110).
- 7.8 mg capsule: Each capsule contains 7.8 mg iron and the following excipient(s) with known effect: lactose, Allura Red AC (E129) and Sunset Yellow FCF (E110).

A full list of excipients can be found in the Investigator's Brochure.

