3 STUDY ENDPOINTS

3.1 Primary Endpoints

The primary endpoints for the study are pharmacokinetic parameters.

1. Population PK analysis of maltol and maltol glucuronide in plasma from PK samples collected on Day 1 (after first morning dose) and Day 10 (after last morning dose). Parameters to be derived and reported for each Ferric Maltol dose are:
 - C_{max} , $C_{ave(0-6h)}$, $AUC_{(0-6h)}$, and $AUC_{(0-Inf)}$ on Day 1 and Day 10 and ratios of Day 10/Day 1 for these parameters;
 - T_{max} ;
 - Half-life ($t_{1/2}$);
 - Apparent systemic clearance (CL/F); and
 - Apparent volume of distribution (V/F).

Plasma concentrations, including C_{trough} of maltol and maltol glucuronide by time of collection on Day 1 and Day 10 will also be presented.

2. Descriptive and population PK analysis of serum iron and TSAT from PK samples collected on Day 1 and Day 10. Parameters to be derived and reported for each Ferric Maltol dose are:
 - Change from pre-dose (C_{trough}) to maximum post-dose (C_{max}) value for serum iron and TSAT; $C_{ave(0-6h)}$;
 - Pre-dose adjusted Incremental $AUC_{(0-6h)}$ on Day 1 and Day 10 from a population PK analysis approach, and percent change from Day 1 to Day 10; and
 - Apparent systemic clearance (CL/F), apparent volume of distribution (V/F).

Serum iron and TSAT by time of collection on Day 1 and Day 10 will also be presented.

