4.2.2 PK Parameters

PK samples were to be collected on Day 1 and Day 10, pre-dose and post-dose according to the PK Sample Schedule Group that the subject was assigned to.

Maltol (ng/dL) and Maltol Glucuronide (µg/mL) results will be available from the data export from the bioanalytical laboratory, ABS Laboratories Ltd.

Serum iron (µmol/L) and TSAT (%) will be available from the standard export from Medpace Reference Laboratory (MRL). The data transport files from MRL will contain serum iron and

TSAT in the standard reporting units of the reporting laboratory and in Système International d'Unités (SI) units.

C_{\max} , $C_{\text{ave}(0-6h)}$, $AUC_{(0-6h)}$, $AUC_{(0-\infty)}$, T_{\max} , half-life ($t_{1/2}$), apparent systemic clearance (CL/F), apparent volume of distribution (V/F) and C_{trough} will be derived for maltol, maltol glucuronide, serum iron and TSAT at Day 1 and Day 10.

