$R_{AUC0-6h}$	Accumulation ratio based on AUC_{0-6} after first dose and last dose, calculated as $AUC_{0-6(Day10)}/AUC_{0-6(Day1)}$

Pharmacokinetic parameters of maltol and maltol glucuronide will be listed by dose group for each individual subject and summarized by dose group using the following descriptive statistics: n (the number of subjects), arithmetic mean, SD (standard deviation), geometric mean, geometric CV (coefficient of variation), median, minimum and maximum.

Plasma concentration-time courses of maltol/maltol glucuronide on Day 1 and Day 10, including C_{trough} , will be tabulated and graphically displayed per subject and summary statistics will be provided for each dose group for a specific timepoint/day. Plots of mean and geometric mean and plots with combined individual time courses will be provided by dose group.

Actual and/or dose-normalized pharmacokinetic parameters of C_{max} and AUCs will be graphically displayed for maltol and maltol-glucuronide as function of the dose, to explore dose-proportionality.

Serum iron and TSAT:

The following parameters for serum iron and TSAT on Day 1 will be derived for each subject based on the uncorrected and baseline-corrected predicted serum iron concentrations and TSAT, if applicable:

Table 6 Parameters for Serum Iron and TSAT on Day 1

Parameters	Description
C_{\max}	Maximum plasma concentration directly from data
C_{trough}	Pre-dose plasma concentration
Change from C_{trough} to C_{\max}	$C_{\max} - C_{\text{trough}}$
T_{\max}	Time to reach C_{\max}
λ_z	Apparent first-order terminal elimination rate constant
AUC_{0-6h}	Area under the plasma concentration versus time curve from time zero to 6 h using the pre-dose adjusted concentration data
$AUC_{0-\infty}$	Area under the plasma concentration versus time curve from time zero extrapolated to infinity time using the pre-dose adjusted concentration data
CL/F	Apparent clearance calculated as Dose/ $AUC_{0-\infty}$
V_z/F	Apparent volume of distribution (as Dose/ $[\lambda_z * AUC_{0-\infty}]$)

The following parameter for serum iron and TSAT on Day 10 will be derived for each subject based on the uncorrected and baseline-corrected predicted serum iron concentrations and TSAT, if applicable:

Table 7 Parameters for Serum Iron and TSAT on Day 10

Parameters	Description
Tau	The dosing interval for steady-state data tau=12
C_{\max}	Maximum concentration between dose time and dose time + Tau. If not unique, then the first maximum is used.

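### CL/F and V/F are named primary parameters for TSAT, but TSAT is a percentage, so the planned formulas give neither a clearance nor a volume

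*SAP*

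**What the plan says.** Protocol 6.3 defines primary endpoint 2 as "Descriptive and population PK analysis of serum iron and TSAT from PK samples collected on Day 1 and Day 10". CL/F and V/F are among its parameters, and nothing confines them to serum iron. Protocol 12.2.1 repeats the list. SAP 3.1 carries it over: "Apparent systemic clearance (CL/F), apparent volume of distribution (V/F").

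SAP 4.2.2 removes any doubt about the analytes. It lists Cmax, AUCs, half-life, CL/F, V/F and others, and says they "will be derived for maltol, maltol glucuronide, serum iron and TSAT at Day 1 and Day 10". The same section gives the units: "Serum iron (µmol/L) and TSAT (%) will be available from the standard export" of the central laboratory.

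The formulas are in SAP 8.5.4, in tables titled for serum iron and TSAT:

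- **Table 6 (Day 1):** CL/F is "Apparent clearance calculated as Dose" divided by AUC0-∞. Vz/F is "Apparent volume of distribution (as Dose" divided by λz × AUC0-∞.
- **Table 7 (Day 10):** CL/F is Dose divided by AUC0-tau. There is no V/F row and no AUC0-∞ row.

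Both tables are introduced with the qualifier *if applicable*. SAP 8.5.1 allows a population PD approach for TSAT if the PPK modelling is not feasible. Its parameters, in Table 8, do not include CL/F or V/F.

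**The concern.** Clearance and volume of distribution relate an amount of substance to its concentration. TSAT is a ratio of iron to binding capacity. There is no amount of TSAT to clear and no volume for it to fill. The formulas will still return numbers, which the SAP would list by subject and summarise by dose group under the labels CL/F and V/F.

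These are named primary parameters, and protocol 5.5 says the data will be used to select the dose or doses for the Phase 3 paediatric study. A reader of the tables could take the TSAT rows as information on the disposition of iron beyond what the serum iron rows give.

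**Working it through.** The plan states no figure to reproduce here. The check is one of units, followed by what the number would represent.

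**Inputs**

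- Dose: mg of iron (protocol 8.1: "30 mg capsule: Each capsule contains 30 mg iron").
- Serum iron in µmol/L and TSAT in % (SAP 4.2.2).
- Formulas from SAP Tables 6 and 7.
- Adult Day 1 group means at 30, 60 and 90 mg (protocol 5.4). Peak serum iron: 32.3, 49.1 and 48.7 µmol/L. Peak TSAT: 45.6, 69.8 and 67.3%. Rise above baseline at 6 h: iron 11.8, 33.0 and 24.3 µmol/L; TSAT 17.0, 47.3 and 33.3%.

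**Step 1: units**

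| Analyte | Dose/AUC | Dose/(λz × AUC) |
|---|---|---|
| Serum iron | µmol ÷ (µmol·h/L) = L/h | L |
| TSAT | mg ÷ (%·h) = mg/(%·h) | mg/% |

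The serum iron row has the units of a clearance and a volume once dose is converted from mg to µmol. The TSAT row does not. Writing TSAT as a fraction changes its units to mg/h and mg, still with no volume.

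**Step 2: what the TSAT number is**

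If TSAT (%) = 100 × serum iron/TIBC, the ratio 100 × iron/TSAT should be a plausible and stable TIBC.

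- From peaks: 32.3/0.456 = 70.8; 49.1/0.698 = 70.3; 48.7/0.673 = 72.4 µmol/L.
- From 6 h rises: 11.8/0.170 = 69.4; 33.0/0.473 = 69.8; 24.3/0.333 = 73.0 µmol/L.

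These are ratios of adult group means, but they agree closely, at about 71 µmol/L. With TIBC constant over the profile and both curves baseline-adjusted in the same way, AUC(TSAT) = 100 × AUC(iron)/TIBC. Therefore

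Dose/AUC(TSAT) = CL/F(iron) × TIBC/100.

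**Step 3: illustration (assumed values)**

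Take a 30 mg dose, an assumed incremental iron AUC of 60 µmol·h/L, and assumed TIBC of 50, 71 and 90 µmol/L. With the atomic mass of iron at 55.845, the dose is 30,000/55.845 = 537.2 µmol.

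- Iron CL/F = 537.2/60 = 8.95 L/h in all three cases.
- AUC(TSAT) = 100 × 60/TIBC = 120, 84.5 and 66.7 %·h.
- TSAT value = 30/AUC(TSAT) = 0.250, 0.355 and 0.450 mg/(%·h).

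The ratio of largest to smallest is 90/50 = 1.8 with identical iron kinetics. That figure depends on the assumed TIBC range. Step 1 depends on no assumption.

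**Step 4: does anything in the SAP exclude these values?**

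The qualifier *if applicable* is not defined. It also introduces the maltol tables (Tables 4 and 5), where CL/F is a legitimate parameter, so it cannot be read as excluding TSAT. SAP 4.2.2 carries no such qualifier. The PPD route depends on feasibility of the PPK model, not on whether its parameters have meaning for TSAT.

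**The case against.** The strongest reply is that little depends on these rows. The analyses are descriptive, SAP Section 13 states that no formal sample size calculation was done, and no decision rule uses TSAT CL/F or V/F. The dose-proportionality displays use Cmax and AUCs. The interpretable TSAT measures are already planned, and Table 8 shows that the authors had a response-type parameter set in mind. All of this stands, and it limits the harm to uninterpretable table rows. It does not make the rows right.

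Several stronger readings are tempting, and the documents do not support them:

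- *TSAT CL/F reflects binding capacity instead of iron handling.* By the identity in Step 2 it mixes both. In the adult means the implied TIBC varies across doses by only about 3% at peak (72.4/70.3) and 5% at 6 h (73.0/69.4), so by-dose summaries may be little distorted by TIBC if that carries over to children.
- *Dependence on TIBC is the reason to drop these parameters.* With assumed TIBC of 60 and 80 µmol/L, the TSAT rise differs by 80/60 = 1.33 and the TSAT CL/F by 60/80 = 0.75. The same scaling affects the TSAT change, Cave and incremental AUC, which are worth keeping. Only the unit argument separates the two sets.
- *The PD route opens only if the PPK fit fails to converge.* The SAP's gloss about convergence belongs to the choice of estimation method. For TSAT the trigger is feasibility, left undefined.
- *TSAT must be analysed with a response model.* A compartmental fit can serve as an empirical curve for predicting the TSAT profile; that choice is separate from reporting CL/F and V/F.

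**Conclusion.** The point holds on units alone. For TSAT, the planned CL/F and Vz/F are in mg/(%·h) and mg/%, are not a clearance or a volume, and amount to an inverse dose-normalised response. A feasible PPK fit would still produce them as primary results. The conclusion needs only the stated units and formulas. The approximation iron CL/F × TIBC/100 further assumes constant TIBC and like baseline adjustment, and the 1.8-fold illustration rests on assumed values.

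The reach is modest. Volume for TSAT arises in Table 6 only, although SAP 4.2.2 promises it on Day 10 as well. A reader might infer that the TSAT endpoint as a whole is compromised; it is not, because change from pre-dose to maximum, Cave(0-6h) and incremental AUC(0-6h) are valid measures for a percentage.

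**What to change.** - In SAP Table 6, limit CL/F, Vz/F and AUC0-∞ to serum iron. For TSAT, the extrapolated AUC serves only as the denominator of the other two. In Table 7, limit CL/F to serum iron.
- Make the same restriction in SAP 3.1 and 4.2.2, and in 4.2.2 resolve the promise of a Day 10 V/F that Table 7 does not contain.
- Restrict CL/F and V/F to serum iron in primary endpoint 2 in protocol 6.3 and 12.2.1, with the synopsis to match.
- Record the change in SAP Section 14, which currently declares none.
- Keep change from pre-dose to maximum, Cave(0-6h) and incremental AUC(0-6h) for TSAT. The choice between a PPK-type and a response-type model for the TSAT profile can stay as planned.

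The cost is a wording change to a protocol endpoint, which is more than an SAP edit, and fewer table rows. No interpretable TSAT result is lost.

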3 ABBREVIATION INDEX

AE	Adverse Event
ALT	Alanine Aminotransferase
ANCOVA	Analysis of Covariance
AST	Aspartate Aminotransferase
AUC	Area Under the Plasma Concentration Curve
AUC _(0-6h)	Area Under the Plasma Concentration Curve for 0-6h
AUC _(0-inf)	Area Under the Plasma Concentration Curve for 0-infinity
BID	Twice Daily
BUN	Blood Urea Nitrogen
C	Celsius
CA	Competent Authority
C _{ave(0-6h)}	Average Steady State Plasma Concentration from 0-6h
CD	Crohn's Disease
CHR	Reticulocyte Haemoglobin Concentration
C _{max}	Maximum Plasma Concentration
CL/F	Apparent Systemic Clearance
CRF	Case Report Form
CRO	Contract Research Organisation
CRP	C-Reactive Protein
CS	Clinically Significant
CSR	Clinical Study Report
C _{trough}	Minimum Plasma Concentration
ECG	Electrocardiogram
eGFR	Estimated Glomerular Filtration Rate
ESA	Erythropoiesis Stimulating Agent
FOCE	First Order Conditional Estimation
FO	First Order Estimation
GCP	Good Clinical Practice
GGT	Gamma-Glutamyl Transpeptidase
GI	Gastrointestinal
GMP	Good Manufacturing Practice
h	Hour
Hb	Haemoglobin
IBD	Inflammatory Bowel Disease
ICH	International Conference on Harmonisation
ID	Iron Deficiency
IDA	Iron Deficiency Anaemia
IEC	Independent Ethics Committee
IMP	Investigational Medical Product
IMPD	Investigational Medicinal Product Dossier
IRB	Institutional Review Board

ITT	Intention-To-Treat
IV	Intravenous
MCH	Mean Cell Haemoglobin
MCHC	Mean Cell Haemoglobin Concentration
MCV	Mean Cell Volume
NCS	Non-Clinically Significant
NTBI	Non-Transferrin Bound Iron
OFP	Oral Ferrous Product
PHI	Protected Health Information
PK	Pharmacokinetics
PPK	Population Pharmacokinetics
PP	Per Protocol
PR	Electrocardiogram PR Interval
QRS	Electrocardiogram QRS Duration
QT	Electrocardiogram QT Interval
RR	Electrocardiogram RR Interval
SAE	Serious Adverse Event
SAP	Statistical Analysis Plan
$t_{1/2}$	Half-life
TIBC	Total Iron Binding Capacity
T_{max}	Time to Maximum Plasma Concentration
TNF α	Tumor necrosis factor alpha
TSAT	Transferrin Saturation
UC	Ulcerative Colitis
UIBC	Unsaturated Iron Binding Capacity
V/F	Apparent Volume of Distribution
WHO	World Health Organisation
yrs	Years

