The pharmacokinetics (PK) and iron uptake of 30mg Ferric Maltol BID were confirmed in a cohort of 15 IBD patients participating in the open-label phase of studies ST10-01-301 and ST10-01-302 (Shield TX, data on file for sub-study ST10-01-102). Plasma concentrations of maltol above the limit of assay detection were transiently observed between 15min and 4h after dosing (mean Cmax 67.3ng/mL; median Tmax 1.0h; mean AUC 136h*ng/mL; mean t1/2term 0.8h). However, consistent with earlier studies of Ferric Maltol, maltol glucuronide predominated in plasma (mean Cmax 4677ng/mL; median Tmax 1.0h; mean AUC 9651h*ng/mL and mean t1/2term 1.1h). Maximal change in serum iron and TSAT was observed 2h after dosing, however in many subjects it was apparent from the TSAT rises that iron uptake was occurring from 30 minutes. The inter-subject variability for AUC of both maltol and maltol-glucuronide in this cohort was low (approximately 27%).

Another open-label, randomised Phase 1 study evaluated the pharmacokinetics of Ferric Maltol and its effect on iron indices in patients with iron deficiency (with or without anaemia). Twenty-four subjects received Ferric Maltol 30, 60, or 90 mg BID over an 8-day period. Pharmacokinetics and iron uptake were assessed on Days 1 and 8. Ferric maltol showed predictable pharmacokinetics, no accumulation over 7 days, and improvements in iron uptake across the dose range 30–90 mg BID (Bokemeyer, 2016). Maximum serum concentrations of total iron were reached between 2 and 3 hours' post-dose. Initially a slight decline in serum total iron concentrations was observed, followed by an increase to on average 32.3, 49.1 and 48.7 μ mol/L on Day 1 for the 30 mg, 60 mg and 90 mg BID dose groups, respectively. Serum total iron concentrations gradually declined after reaching Tmax and mean serum concentrations were 11.8, 33.0 and 24.3 μ mol/L above baseline at 6 hours' post-dose on Day 1 for the 30 mg, 60 mg and 90 mg BID dose groups, respectively. Comparable serum concentrations were measured on Day 8. Plots comparing total iron and the exposure to maltol and maltol glucuronide showed no clear relationship.

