Maximum serum values of TSAT were reached between 2 and 3 hours' post-dose. TSAT values gradually increased up to an average value of 45.6, 69.8 and 67.3% on Day 1 for the 30 mg, 60 mg and 90 mg BID dose groups, respectively. TSAT gradually declined after reaching Tmax and serum values were 17.0, 47.3 and 33.3% above baseline at 6 hours' post-dose on Day 1 for the 30 mg, 60 mg and 90 mg BID dose groups, respectively. Similar TSAT serum values were measured on Day 8. Plots comparing TSAT and the exposure to maltol and maltol glucuronide showed no clear relationship.

Both serum iron concentration and TSAT increased after dosing, with maximum values between 1.5 and 3 hours' post dose. Iron absorption appeared to plateau at 60mg BID. There was no clear relationship between either total serum iron or TSAT and exposure to maltol or maltol glucuronide. Total serum iron concentrations and TSAT values were generally higher with increasing ferric maltol doses and were comparable after a single dose and at steady-state.

Plasma concentrations of both maltol and maltol glucuronide increased rapidly after dosing, reaching Cmax in around 1 to 1.5 hours' post dose, before declining to baseline levels between 3 and 6 hours. Exposure to maltol glucuronide was considerably higher than exposure to maltol for all ferric maltol dosing regimens. The mean amount of unchanged maltol excreted in urine over 6 hours (Ae0-6h) on Day 1 was very low: 0.1, 0.2 and 0.4 mcg for the 30 mg, 60 mg and 90 mg dose groups, respectively, representing approximately 0.05, 0.04 and 0.07% of the administered dose. The mean renal clearance ranged between 2.5 and 15 L/hour. Urine PK parameters were generally comparable between Day 1 and Day 8. The mean amount of maltol glucuronide excreted in urine over 6 hours on Day 1 was 197, 403 and 870 mg for the 30 mg, 60 mg and 90 mg BID dose groups, respectively, representing approximately 40.8, 41.7 and 60.6% of the administered dose. The mean renal clearance ranged between approximately 20 to 27 L/hour for the different dose groups. Urine PK parameters were generally comparable between Day 1 and Day 8.

Unlike serum iron, maltol absorption appeared to be dose proportional. These data are consistent with the iron and maltol absorption profiles reported in the early unpublished/published clinical data and the published non-clinical data.

Refer to the Investigator Brochure for further information.

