5.5.2 Study Treatment Duration

Subjects will receive twice daily (morning and evening) Ferric Maltol (7.8mg, 16.6mg or 30mg) for 9 days (Days 1 to 9) and final single dose on the morning of Day 10.

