4.2 Primary Pharmacokinetic Measurements and Variables

4.2.1 PK blood sampling

On study days 1 and 10, all subjects were to have baseline (pre-dose) PK blood samples collected immediately prior to Ferric Maltol dosing (0h). Subjects were then to have further PK blood samples collected at two additional times between 0.5h and 6h after dosing on Days 1 and 10; within each Ferric Maltol dose group (7.8 mg, 16.6 mg or 30 mg BID), the post-dose PK sample time collection windows were 0.5-1h, 1.0-2.0h, 2.0-3.0h, 3.0-4.0h and 4.0-6.0h. The 12 subjects within each Ferric Maltol dose group were assigned to the required post-dose PK blood sampling schedule in sequential order at the time of randomisation, based on current subject enrolment across all study sites. Table 3 details the sparse PK blood sample schedule.

Table 3 Sparse PK Blood Sampling Schedule

	PK Sample Schedule			
	Group 1 (N = 3/12)	Group 2 (N = 3/12)	Group 3 (N = 3/12)	Group 4 (N = 3/12)
Pre-dose (0h)	X	X	X	X
0.5 – 1h	X	X		
1.0 – 2.0h	X		X	
2.0 – 3.0h		X		X
3.0 – 4.0h			X	
4.0 – 6.0h				X

For each individual subject, the post-dose PK blood sampling schedule was to be the same on Day 1 and Day 10. Post-dose samples for each subject were to be collected within the allocated time-windows (e.g. between 0.5-1h or 1-2h); the exact time of the sample collection was to be recorded in the eCRF. For those subjects in PK Sample Schedule Group 1 (see Table 3), the PK blood samples for the 0.5-1h timepoint window were to be taken at 30 minutes prior to the PK blood samples for the 1-2h timepoint window on Day 1 and Day 10, to provide an adequate spread of actual sampling times for the population PK analysis.

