C_{trough}	Minimum concentration between dose time and dose time + Tau
Change from C_{trough} to C_{\max}	$C_{\max} - C_{\text{trough}}$
AUC_{0-6h}	Area under the plasma concentration versus time curve from time zero to 6 h using pre-dose adjusted concentration data
$AUC_{0-\tau}$	Area under the plasma concentration versus time curve from time zero to Tau
$C_{\text{ave}(0-6h)}$	Average Steady State Plasma Concentration from 0-6h, calculated as AUC_{0-6h} divided by 6
CL/F	Apparent clearance calculated as Dose/ $AUC_{0-\tau}$
$R_{C_{\max}}$	Accumulation ratio based on maximum concentrations after first dose and last dose, calculated as $C_{\max\text{Day10}}/C_{\max\text{Day1}}$
$R_{AUC0-6h}$	Accumulation ratio based on AUC_{0-6} after first dose and last dose, calculated as $AUC_{0-6(\text{Day10})}/AUC_{0-6(\text{Day1})}$

Pharmacokinetic parameters of serum iron and TSAT will be listed by dose group for each individual subject and summarized by dose group using the following descriptive statistics: n (the number of subjects), arithmetic mean, SD (standard deviation), geometric mean, geometric CV (coefficient of variation), median, minimum and maximum.

Concentration-time courses of serum iron and TSAT on Day 1 and 10, including C_{trough} on Day 1 and 10 will be tabulated and graphically displayed per subject and summary statistics will be provided for each dose group and visit/timepoint. Plots of mean and geometric mean and plots with combined individual time courses will be provided by dose group.

Actual and/or dose-normalized pharmacokinetic parameters of C_{\max} and AUCs will be graphically displayed for serum iron and TSAT as function of the dose, to explore dose-proportionality.

If the PPK model is not feasible for TSAT and PPD model is used for TSAT, the following parameters for TSAT on Days 1 and 10 will be derived for each subject based on the predicted TSAT, if applicable:

Table 8 Parameters for TSAT on Days 1 and 10

Parameters	Description
Baseline	Baseline response value before dosing
R _{max}	Maximum response value
R _{min}	Minimum response value
T _{max}	Time to reach R _{max}
T _{min}	Time to reach R _{min}
AUC _{0-6h}	Area under the effect versus time curve from time zero to 6 h
AUC _{0-24h}	Area under the effect versus time curve from time zero to 24 h
AUC_Above_B	Area under the response curve that is above the baseline
AUC_Below_B	Area that is below the baseline and above the response curve
AUC_Net_B	= AUC_Above_B - AUC_Below_B

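### SAP Table 7 measures the Day 10 change in serum iron and TSAT from the 0–12 h minimum, whereas the primary endpoint and Table 6 measure it from the pre-dose value

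*SAP*

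**What the plan says.** Protocol 6.3 lists, among the primary parameters, "Change from pre-dose (C_{trough}) to maximum post-dose (C_{max}) value for serum iron and TSAT". Protocol 12.2.1 and SAP 3.1 repeat it, and none of the three gives a separate rule for Day 10.

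SAP 8.5.4 turns this into two tables. In Table 6 (Day 1), Ctrough is "Pre-dose plasma concentration" and the change is Cmax minus Ctrough. In Table 7 (Day 10), the change has the same formula, but Ctrough is "Minimum concentration between dose time and dose time + Tau". Table 5 uses the same wording for maltol and maltol glucuronide, and the abbreviation lists of both documents gloss Ctrough as "Minimum Plasma Concentration". SAP section 14 declares no change from the protocol.

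In Table 6 both AUC rows, including the AUC0-inf behind Day 1 CL/F, are labelled pre-dose adjusted. In Table 7 AUC0-6h carries that label. AUC0-tau, which gives Day 10 CL/F, does not. The sentences introducing the two tables say that parameters come from both uncorrected and baseline-corrected predictions, without saying which version of CL/F is the reported one.

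**The concern.** One primary parameter has two definitions. The endpoint names the pre-dose value in words and Table 6 applies it, but Table 7 lets the starting point move to wherever the predicted curve is lowest in the 12 h after the dose. A reader comparing Day 1 with Day 10 would take the two changes as like for like, and they are not.

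Two things could separate the interval minimum from the pre-dose value. Dosing is described only by time of day ("Subjects will receive twice daily (morning and evening) Ferric Maltol"), so the overnight gap may be shorter than 12 h, and the predicted value at 12 h would then lie below the pre-dose value. Serum iron may also fall before it rises: for the adult dose-ranging study Protocol 5.4 reports "Initially a slight decline in serum total iron concentrations was observed".

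The study is meant to inform dose selection for Phase 3, so its primary parameters should be computed as stated. The missing AUC0-tau label is a lesser matter. It leaves open whether the reported Day 10 CL/F contains endogenous iron.

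**Working it through.** The plan states no figure to reproduce, so the check is algebra followed by an illustration.

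**Direction.** The window from dose time to 12 h contains dose time, so Cmin ≤ Cpre and

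Cmax − Cmin = (Cmax − Cpre) + (Cpre − Cmin) ≥ Cmax − Cpre.

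If a constant B is subtracted, (Cmax − B) − (Cmin − B) = Cmax − Cmin. The baseline-corrected version therefore gives the same number and does not restore the endpoint.

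**Size: inputs.** From Protocol 5.4 (adults, 30 mg, Day 1): mean peak 32.3 µmol/L, mean 11.8 µmol/L above baseline at 6 h, peak between 2 and 3 h. Assumed, because the documents do not give them: baseline b = 5, 10 or 15 µmol/L, peak at 2.5 h, a linear rise then log-linear decline of the increment, and linear superposition of the 18 doses on Days 1–9.

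The peak increment is P = 32.3 − b, and λ = ln(P/11.8)/3.5 = 0.240, 0.182 and 0.109 per h.

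**Worked case, b = 10, overnight gap 10 h, no lag** (P = 22.3, λ = 0.1819):
- Carry-over at dose time = 22.3 × (e^(−7.5λ) + e^(−21.5λ)) / (1 − e^(−24λ)) = 6.23, so Cpre = 16.23.
- Cmax at 2.5 h = 10 + 22.3 + 6.23 × e^(−2.5λ) = 36.25.
- Value at 12 h = 10 + 22.3 × e^(−9.5λ) + 6.23 × e^(−12λ) = 14.67, which is the minimum.
- Ratio = (36.25 − 14.67)/(36.25 − 16.23) = 21.58/20.02 = 1.078.

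**All cases**, Table 7 change divided by pre-dose change, for b = 5/10/15:

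| Overnight gap | No lag | 1 h lag |
|---|---|---|
| 14 h | 1.000 | 1.015/1.026/1.047 |
| 13 h | 1.000 | 1.019/1.030/1.052 |
| 12 h | 1.000 | 1.024/1.036/1.057 |
| 11 h | 1.028/1.035/1.037 | 1.031/1.043/1.063 |
| 10 h | 1.065/1.078/1.079 | same |
| 9 h | 1.113/1.132/1.128 | same |

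A 0.5 h lag at 12 h gives 1.013/1.019/1.029. Moving the peak to 2 or 3 h, without lag, gives 1.06–1.09 at 10 h and 1.11–1.15 at 9 h.

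**Early dip, no carry-over.** For a dip d below pre-dose the ratio is (P + d)/P with P = 27.3/22.3/17.3. The protocol gives no size for the dip. Assuming d = 0.5, 1 or 2 µmol/L gives 1.02–1.03, 1.04–1.06 and 1.07–1.12.

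**CL/F label.** Uncorrected AUC0-tau equals corrected AUC0-tau plus 12 × baseline, so uncorrected CL/F divided by corrected CL/F is AUCcorr/(AUCcorr + 12b). With superposition at a 12 h gap and b as the untreated baseline: 148.0/208.0 = 0.71, 150.5/270.5 = 0.56, 179.9/359.9 = 0.50. Without carry-over: 136.3/196.3 = 0.69, 128.7/248.7 = 0.52, 123.9/303.9 = 0.41. For TSAT (adult peak 45.6%, 17.0 points above baseline at 6 h, no carry-over) the fraction runs from 206.0/266.0 = 0.77 (assumed baseline 5%, peak at 2 h) to 175.3/355.3 = 0.49 (15%, 3 h).

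The day of the baseline matters too if there is carry-over. With b = 10 and a 12 h gap, the Day 10 pre-dose value is 10 + 22.3 × e^(−9.5λ)/(1 − e^(−12λ)) = 14.47. Subtracting it instead of 10 cuts the corrected AUC from 150.5 to 150.5 − 12 × 4.47 = 96.9.

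**The case against.** The strongest reply is that at steady state on a regular 12 h regimen the predicted pre-dose value is the interval minimum, so the two definitions agree. The no-lag results of 1.000 at 12, 13 and 14 h bear this out. No document states a 9 or 10 h overnight gap, and withholding the Day 10 dose until the site visit tends to lengthen the gap. A constant baseline with first- or zero-order input, among the models listed in SAP 8.5.1, cannot fall below baseline without carry-over, so the adult dip may never appear in the predictions, although the SAP leaves other models open. Protocol 5.4 adds that adult iron and TSAT values "were comparable after a single dose and at steady-state", which argues against much carry-over. All of this stands, and it limits the size of the effect.

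The reply that Ctrough simply means minimum has some support in Table 5 and the abbreviation lists. It does not rescue Table 7, because the endpoint says pre-dose in words.

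A reader might infer that Table 7 swaps an observed value for an extrapolated one, since SAP 4.2.1 has "further PK blood samples collected at two additional times between 0.5h and 6h after dosing on Days 1 and 10" and none later. That overstates the contrast: under SAP 8.5.4 the pre-dose value is model-predicted as well. It is only better anchored by data, because every subject has a scheduled pre-dose sample.

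A reader might also infer that Day 10 CL/F will be uncorrected and that SAP 4.3.1 fixes the Day 1 value as baseline. Neither is established. Both versions are to be produced. SAP 4.3.1 names transferrin, TIBC, UIBC and ferritin, not serum iron or TSAT. Note 6 to SAP Table 2 does count those two as iron markers, but Protocol 7.1 and 10.7.4, note 5 to SAP Table 2 and SAP 4.2.1 call the pre-dose samples on both days baseline, and SAP 8.4 does not define the term.

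**Conclusion.** The contradiction is real. As written, the Day 10 change in Table 7 is not the stated primary endpoint, is defined differently from Day 1, and can err only upwards.

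The likely size is small: nothing with an overnight gap of 12 h or more and no lag, about 1 to 6% with a lag of 0.5 to 1 h, and about 6 to 13% only at assumed gaps of 9 to 10 h (up to 15% if the peak is at 3 h). These figures rest on adult means, assumed baselines and linear superposition. They are not forecasts for this trial.

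It would be tempting to conclude that Day 10 uptake will be materially overstated or that accumulation will be misread. The documents do not support that. The analysis is descriptive, the planned Day 10/Day 1 ratios are for Cmax and AUC0-6h only, AUC0-6h is pre-dose adjusted on both days, and SAP 8.4 tabulates observed values and changes from baseline.

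The CL/F point is a missing label. The fractions of 0.41 to 0.77 show what would follow if the uncorrected version were the one reported, not what the plan commits to. Which day's pre-dose value is subtracted remains unsettled.

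**What to change.** - In Table 7, compute the change as Cmax minus the Day 10 pre-dose value, predicted from the same model as in Table 6.
- If the 0–12 h minimum is wanted, report it under a separate name such as Cmin in both Table 7 and Table 5, and align the SAP abbreviation entry, so that Ctrough has one meaning throughout the SAP. Note in the SAP that the protocol's abbreviation list differs.
- State which version of AUC0-tau, uncorrected or baseline-corrected, gives the reported Day 10 CL/F for both serum iron and TSAT. The baseline-corrected version matches Table 6. The other can remain as supporting output.
- State whether the Day 1 or the Day 10 pre-dose value is subtracted on Day 10.

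The cost is a few lines in Tables 5 and 7, one abbreviation entry and one note, plus matching programming before database lock. No new data are needed, and the endpoint wording in the protocol stays as it is.
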